- 3. Daily telephone questionnaires documenting compliance, symptoms, and side effects will be obtained until patients are completely recovered from influenza for 24 hours or reach 21 days from date of enrollment. All daily information will be recorded on a case report form, and then entered into REDCap Cloud.

1 INTRODUCTION

1.1 Background

We propose to conduct a randomized, double-blind, placebo-controlled trial of elderberry extract in a group of 65-100 patients with documented influenza who have been prescribed or offered a prescription for oseltamivir or baloxavir marboxil (Xofluza).

A recent evidence-based systematic review by the Natural Standard Research Collaboration concluded that there is good scientific evidence that elderberry extract supplementation provides effective relief for the symptoms of influenza⁽¹⁻⁴⁾ The fact all previously published elderberry extract supplementation studies have been small, did not have intent-to-treat analysis, and were not published in high impact journals probably helps explain why their findings have not been generally recognized by the medical community and lay-public.

The "CDC estimates that influenza in the United States has resulted in between 9.2 million and 60.8 million illnesses, between 140,000 and 710,000 hospitalizations and between 12,000 and 56,000 deaths annually since 2010.⁽⁵⁾ If elderberry extract supplementation is shown to be associated with improvement of symptoms of influenza there could be a beneficial impact on health in the United States and the world.

1.2 Investigational Agent [if applicable] Information provided by manufacturer describing investigational drug.

See attachments below:

1.3 Preclinical data

A recent review of elderberry describes its potential mechanisms of action. Elderberry has been reported "to modulate the inflammatory cytokines IL-1 and TNF-alpha in vitro, increase human basophil secretion of IL-4, IL-13, and histamine, inhibit macrophage release of proinflammatory cytokines, and contain flavonoids reported to possess antioxidant activity.⁽¹⁾" Sambucol® inhibits influenza A and B, HIV, and herpes simplex in vitro and in a randomized, placebo-controlled trial was associated with increased hemagglutination inhibition titers to influenza B infections in vivo.^(1,2,6)

A small study showed chimpanzees supplemented with prophylactic Sambucol® 10 ml once daily for approximately six months had less than 1/3 the days of flu-like symptoms compared with a placebo supplemented group⁽⁷⁾ When symptoms occurred the dosage was increased to 15 ml twice daily, and the duration of illnesses were twice as long in the placebo group compared to the Sambucol® supplemented group⁽⁷⁾.

Another review of the antiviral properties of black elder products states, Sambucus nigra (black elder) flowers have been approved by Commission E of the German Federal Institute for Drugs and Medical Devices for the treatment of viral infections, but other parts of the plant have not. While the fruit is not on the FDA GRAS (generally recognized as safe, as the flowers are) list or approved by the German Commission E, analysis of flowers and cooked fruit have consistently indicated safety; other parts of the plant are less suitable for use."⁽⁶⁾ Sambucol® uses only cooked fruit from the black elderberry plant.

1.4 Clinical Data to Date

There are four published peer-reviewed randomized double-blind placebo-controlled clinical trials with relevance to the protocol under development. Two, in 27 and 60 patients, demonstrated shortening of the duration of proven influenza by approximately 4 days with elderberry extract supplementation versus placebo (p<0.001 in both studies)^(2,3)

Another trial evaluated 64 patients with three or more of the following "flu-like symptoms": fever, headache, muscle aches, coughing, nasal mucus discharge, and nasal congestion. ⁽⁴⁾ By 48 hours of supplementation, "9 patients (28%) in the elderberry extract supplemented group were void of all symptoms, 19 patients (60%) showed complete relief from some symptoms, and had only one or two mild symptoms" (1/10 on a visual analogue scale). No patient in the placebo group achieved complete recovery, and only 5 patients (16%) showed improvement in one or two symptoms (p<0.001 for all symptoms). Most patients in the placebo group remained the same or worsened over the 48-hour monitoring period.

The fourth study of elderberry extract evaluated supplementation before, during and after air-travel in 312 passengers.(8) More cold episodes occurred in the placebo group (17 vs. 12) but that did not reach statistical significance (p=0.4). "Placebo group participants had a significantly longer duration of cold episode days 117 vs.57, p=0.02) and the average symptom score over these days was also significantly higher (583 vs. 247, p=0.05)."

A fifth study, by A. Rao and L. Vitetta, entitled "A prospective, double-blind, randomized, placebocontrolled study to evaluate the safety and efficacy of a complementary medicine formulation, to help reduce duration and severity of cold and flu symptoms in otherwise healthy adults", with a goal of enrolling 120 cold and 80 flu episodes, completed enrollment in Australia on 5/22/2017. Preliminary results shared by [name]. of PharmaCare® in Australia were, "Cold and Influenza relief: cold and influenza duration reduced by 30% (3 day equiv). Symptom severity 35% reduction (participants felt better, faster) using 15mL 4x daily."

1.5 Dose Rationale and Risk/Benefits

The route of administration, dosage, dosage regimen, and dosage period rationale is based upon two previous studies using Sambucol® supplementation for influenza. ^(2, 3) Sambucol® supplementation decreased duration of symptoms by approximately 4 days. The only side effect reported in these studies was bad taste in one patient. The only reported side effects in the 312 air travelers study were 3 placebo patients each with one symptom, either itchy throat, fatigue, or kidney pain, and 2 elderberry patients, one with fatigue and one with cold symptoms. Also, there have been twenty-six years of clinical experience with Sambucol® as an over-the-counter supplement now available on six continents, with 21 years availability in the United States. There are no reported serious adverse effects, and dosage recommendations outside the United States are available for ages 2 and above (http://www.cpginteractive.com/sam/faqs.html) and for ages 5 and above in the United States. Subjects' risks under this protocol are minimal, and the potential benefits to the subjects and society are great.

2 STUDY OBJECTIVES

Determine if elderberry extract supplementation shortens the duration and decreases the severity of influenza symptoms in patients who have been prescribed or offered a prescription of oseltamivir or baloxavir marboxil (Xofluza) for documented influenza infection.

3 STUDY DESIGN

3.1 General Design

This is a Phase IV randomized, double-blind, placebo-controlled trial of elderberry extract supplementation versus placebo. Sixty-five to one hundred patients with Roche^R cobas^R Liat^R polymerase chain reaction documented influenza, with at least 2 moderate influenza symptoms as defined below, and who have been prescribed or offered a prescription for oseltamivir or baloxavir marboxil will be randomized to also receive elderberry extract supplementation or placebo.

3.2 Study Endpoints

Baseline data will be obtained at time of presentation including eligibility criteria, medical history, and current influenza symptoms.

Symptoms will be recorded using the scoring system described in a meta-analysis of "all published and unpublished Roche-sponsored randomized placebo-controlled, double-blind trials of oseltamivir treatment in adult influenza" (⁹). "The primary outcome will be time to alleviation of all symptoms. Seven influenza symptoms (nasal congestion, sore throat, cough, aches and pains, fatigue, headaches, and chills or sweats)" will be graded by severity as "absent" (0), "mild" (1), "moderate" (2), or "severe" (3). Alleviation will be defined to arise when all symptoms scored as absent or mild, and remain so for at least 21.5 hours." The secondary endpoints will be the time to alleviation and to complete resolution of individual and all symptoms. Patients will be followed daily until all symptoms have completely resolved and fever has remained less than 100° F for 24 hours, or for a maximum of 21 days if symptoms have not yet completely resolved for 24 hours.

3.3 Primary Safety Endpoints

The conditions or symptoms that will be recorded from day of presentation until influenza symptoms are resolved include; dry mouth, bad taste, nausea, vomiting diarrhea, constipation, abdominal pain,, rash, difficulty breathing, decreased drinking, dizziness and any other symptoms not previously recorded under study endpoints as outlined above. Patient symptoms and severity of illness will be monitored daily using the Division of AIDS Table for Grading the Severity of Adult and Pediatric Adverse Events ("DAIDS AE GRADING TABLE). See appendix one for all case report forms. Study patients will be asked to call for any worsening influenza symptoms or new conditions or symptoms reaching Grade 3 or 4. See also section 8 safety and adverse events.

4 SUBJECT SELECTION AND WITHDRAWAL

4.1 Inclusion Criteria

Patients are eligible to be included in the study if they meet all of the following criteria:

- [1] Males or females \geq 5 years of age
- [2] With 48 hours or less of an influenza illness documented by polymerase chain reaction
- [3] Have AT LEAST 2 of the following 7 influenza symptoms (nasal congestion, sore throat, cough, aches and pains, fatigue, headaches, and chills or sweats) graded as either moderate or severe
- [4] Have been prescribed or offered a prescription of oseltamivir or baloxavir marboxil (Xofluza)

- [5] Have access to a phone
- [6] Subjects are capable of giving informed consent or have an acceptable legally authorized representative capable of giving consent on the subject's behalf with informed assent given by subject.

4.2 Exclusion Criteria

Patients will be excluded from the study if they meet **any** of the following criteria:

- [1] Known allergy to elderberry extract, oseltamivir, or baloxavir marboxil (Xofluza)
- [2] Use of antibiotic or antiviral medication on presentation to the study
- [3] Women who are pregnant, breastfeeding women, or do not agree to appropriate contraception (abstinence, hormonal, intrauterine device, and barrier) to prevent pregnancy during the study.
- [4] Patients with HIV
- [5] Patients with cystic fibrosis
- [6] Patients currently taking Elderberry Extract or Sambucol

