5.6 Prior and Concomitant Therapy

All medications taken at study enrollment will be recorded on the case report forms and then into REDCap Cloud, and any changes in medications will be recorded daily throughout the study. All patients

will be discouraged from taking any cold or flu preparations except for acetaminophen and ibuprofen as needed for pain and/or fever until they have completed the study and are completely well.

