6 STUDY PROCEDURES

6.1 Pre-registration and Screening

If patients are eligible and interested in participating we will review the informed consent with them, and their families if necessary, and obtain written informed consent or assent, depending upon patients' ages.

6.2 Visit 1

Visit 1 will be completed at the same visit for registration and screening. A nasopharyngeal swab will be obtained for Roche^R cobas^R Liat^R PCR assays for influenza A&B prior to enrollment in study to confirm all study patients have documented influenza.

Informed consent, and assent when indicated, will be obtained prior to completing any study related assessments. Eligibility for the study will be confirmed and baseline data will be obtained.

All women of childbearing potential will have a urine pregnancy test before starting and upon completion of the study. Pregnancy tests will be done following standard Cleveland Clinic operating procedures and documented in the electronic medical record, the case report forms and REDCap Cloud. The result of the pregnancy test(s) will be disclosed to the minor subject and their parent(s)/legal guardian.

Patients will be instructed on how to return unused study medication in the provided stamped envelope addressed to the study coordinator, and for women of childbearing potential how to obtain an end of study pregnancy test at the most convenient Cleveland Clinic laboratory.

Patients will be given their randomly assigned study medication and instructed to give 15 ml of medication, in a measuring cup provided, 4 times a day for 5 days for ages 13 and above and 15 ml 2 times a day for ages 5-12 for 5 days. They will be given their first dose of study medication prior to leaving the emergency room.

Patients will be asked to please avoid taking any additional cold or influenza medications if possible. They will be told they may take ibuprofen or acetaminophen for pain or fever. They will be asked to report daily all medications taken not reported on their day 1 visit. Taking additional medications will not disqualify patients from the study other than taking prescription antibiotics or antivirals prior to the start of the study.

Patients will receive daily phone calls to remind them to take each dose of their study medication and to answer their daily surveys (see Appendix 1). All patients who do not answer their daily surveys on the first call, will receive two additional phone call attempts to have the survey answered.

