14 ATTACHMENTS

14.1 Screening/Enrollment Questionnaire

SCREENING/ENROLLMENT QUESTIONNAIRE

Inclusion Criteria

Mark if Yes

- 1) ____Patients ages 5 and above
- 2) _____With 48 hours or less of an influenza illness documented by polymerase chain reaction
- 3) _____ Have AT LEAST 2 of the following 7 influenza symptoms (nasal congestion, sore throat, cough, aches and pains, fatigue, headaches, and chills or sweats) graded as either moderate or severe
- 4) _____Who have been prescribed or offered a prescription for oseltamivir or baloxavir marboxil
- 5) _____Who have access to a phone
- 6) _____Subjects are capable of giving informed consent or have an acceptable legally authorized representative capable of giving consent on the subject's behalf with informed assent given by subject.

Exclusion Criteria (mark if NO)

- 1. ____ Known allergy to elderberry extract, oseltamivir or baloxavir marboxil
- 2. _____ Use of antibiotic or antiviral medication on presentation to the study
- 3. ____ Pregnant women
- 4. ____ Breastfeeding women

- 5. ____ Women who do not agree to appropriate contraception (abstinence, hormonal, intrauterine device, and barrier) to prevent pregnancy during the study.
- 6. ____ Patients with HIV
- 7. ____ Patients with cystic fibrosis

CHECK HERE TO CONFIRM ALL ABOVE ARE NEGATIVE CHECK HERE TO CONFIRM URINE PREGNANCY TEST NEGATIVE IF APPLICABLE

Additional Information Recorded on All Patients at the Time of Enrollment

Study number	
Birth Date	
Sex	
Race	
Tobacco use	
Allergies	

High Risk Criteria

Patients considered at high risk from influenza (10) Mark if Yes, Leave Blank if No, then Circle or Write-in specific illness****IF More than one possible Answer

- 1. _____ Adult 65 years of age and older
- 2. ____ Resident of nursing homes and other long-term care facilities
- 3. American Indian or Alaskan Native****

People who have medical conditions including:

- 4. ____ Asthma
- 5. Neurological and neurodevelopmental conditions [including disorders of the brain, spinal cord, peripheral nerve, and muscle such as cerebral palsy, epilepsy (seizure disorders), stroke, muscular dystrophy, or spinal cord injury].****
- 6. Chronic lung disease (such as chronic obstructive pulmonary disease [COPD])*****
- 7. Heart disease*****
- 8. _____ Blood disorders (such as sickle cell disease) *****
- 9. Endocrine disorders (such as diabetes or thyroid) *****
- 10. ____Kidney disorders****
- 11. ____ Liver disorders****

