- 12. ____ Metabolic disorders (such as inherited metabolic disorders and mitochondrial disorders)*****
- 13. ____ Weakened immune system due to disease or medication (such as people with cancer, or those on 20 mg/day of prednisone or more for more than 14 days)****
- 14. ____ People younger than 19 years of age who are receiving long-term aspirin therapy
- 15. ____ People with extreme obesity (body mass index [BMI] of 40 or more)

PLEASE LIST ALL MEDICATIONS AND DOSAGES AND HOW OFTER YOU TAKE THE MEDICINE. PLEASE INCLUDE PRESCRIPTION AND OVER-THE-COUNTER MEDICATIONS INCLUDING IBUPROFEN (MOTRIN, ADVIL), ACETAMINOPHEN (TYLENOL), COLD AND FLU PREPARATIONS, AND HERBAL AND OTHER COMPLEMENTARY MEDICATIONS, VITAMINS, MINERALS AND SUPPLEMENTS

All other medical illnesses not previous recorded

Influenza vaccine statu	s up to date YES NO
If NO and <9 y.o. was	one vaccine given this year YES NO
Weight at day of presen	ntation
Highest measured temp	perature during day of presentation
Symptom Score (9):	
0=NONE or Baseline	1=MILD 2=MODERATE 3=SEVERE
Nasal congestion	
Sore throat	
Cough	
Aches and pains	
Fatigue	
Headaches	
Chills and sweats	

Symptoms are graded by severity as "absent" (0), "mild" (1), "moderate" (2), "severe" (3) Presence or absence of possible **other conditions or symptoms at baseline** AND their severity:

SYMPTOM	
SEVERITY OF SYMPTOM	
NONE=0 MILD=1 MODERA	ATE=2 SEVERE=3
BAD TASTE	
DRY MOUTH	
ABDOMINAL PAIN	
NAUSEA	
VOMITING	
DIARRHEA	
CONSTIPATION	
DIZZINESS	
HEADACHE	
RASH	
DIFFICULTY BREATHING _	
DECREASED DRINKING	
LIST ANY OTHERS WITH SH	EVERITY OF ANY SYMPTOM

VITAL SIGNS IN EMERGENCY ROOM, N/A IF ALL NOT AVAILABLE

TEMPERATURE ⁰F WEIGHT

In addition, every day patients are in the study starting from the first contact to the first day they are back to their baseline symptom level they will be asked to use the Division of AIDS (DAIDS) scale for grading the severity of adult and pediatric adverse events version 1.0, December 2004: clarification August 2009. Unlike the Symptom Score above, there are specific definitions of Grades 1-4 as outlined below.

Grade 1 Mild is defined as "Symptoms causing no or minimal interference with usual social & functional activities".

Grade 2 Moderate is defined as "Symptoms causing greater than minimal interference with usual social and functional activity".

Grade 3 Severe is defined as "Symptoms causing inability to perform usual social and functional activity".

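### The exclusion checklist in enrollment form 14.1 omits exclusion 6 (current elderberry use), so a completed form can pass a patient whom section 4.2 excludes

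*Combined protocol and SAP*

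**What the plan says.** **Entry rule.** Section 4.2 excludes a patient who meets any one of six criteria. The sixth is "Patients currently taking Elderberry Extract or Sambucol".

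**Form.** The exclusion checklist in attachment 14.1 has seven lines: allergy, antibiotic or antiviral use, pregnancy, breastfeeding, contraception, HIV and, last, "Patients with cystic fibrosis". Elderberry appears there only as an allergy: "Known allergy to elderberry extract, oseltamivir or baloxavir marboxil". The confirmation box follows directly: "CHECK HERE TO CONFIRM ALL ABOVE ARE NEGATIVE". Later the form asks for a free-text list of all medications, including "COLD AND FLU PREPARATIONS, AND HERBAL AND OTHER COMPLEMENTARY MEDICATIONS, VITAMINS, MINERALS AND SUPPLEMENTS".

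**After entry.** Section 5.6 says that patients "will be discouraged from taking any cold or flu preparations except for acetaminophen and ibuprofen as needed for pain and/or fever". Section 6.2 asks them to avoid other cold or influenza medications where they can. It adds that "Taking additional medications will not disqualify patients from the study", with one exception: prescription antibiotics or antivirals taken before the study starts. The daily questionnaire (14.2) asks for new medications, herbal products and dietary supplements, and the reason each was started.

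**Analysis.** Section 7.2 plans an intent-to-treat comparison with an unequal-variance t-test. Sections 7.2 and 7.3 say nothing about non-study elderberry.

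**The concern.** The checklist is where eligibility is signed off, and its tick box certifies only the items printed above it. The one exclusion it leaves out concerns the investigational product itself. Section 1.5 describes Sambucol as an over-the-counter supplement with 21 years of availability in the United States, so prior use among patients with influenza symptoms is plausible.

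If a current user is enrolled, assigned to placebo and keeps taking the product, that patient is analysed as placebo while receiving something close to the test treatment. Under intent-to-treat, and if elderberry has an effect, the estimated difference shrinks toward zero and a null result becomes harder to interpret. The error runs toward no effect; it does not manufacture a benefit.

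Section 6.2 adds a wording problem. Read literally, its exception names only prior antibiotics or antivirals as disqualifying, although exclusion 6 also makes a product taken before entry disqualifying.

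**Working it through.** **1. Match the lists.**

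| Section 4.2 | Form 14.1 |
|---|---|
| 1 Allergy | line 1 |
| 2 Antibiotic or antiviral use | line 2 |
| 3 Pregnant, breastfeeding, or no agreed contraception | lines 3, 4, 5 |
| 4 HIV | line 6 |
| 5 Cystic fibrosis | line 7 |
| 6 Current elderberry or Sambucol use | none |

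The form's numbering runs 1 to 7 without a break and leads straight into the tick box, so no line has been lost in the text.

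**2. Reproduce the planned sample size.** Inputs from sections 7.1 and 7.2: difference 2 days, SDs 1.3 and 2.5, two-sided alpha 0.05, 90% power, unequal-variance t-test.

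- Variance of the difference at 23 per arm: (1.3² + 2.5²)/23 = 7.94/23 = 0.345, so SE = 0.588.
- Noncentrality: 2/0.588 = 3.40.
- Satterthwaite df: 22 × 7.94²/(1.69² + 6.25²) = 33.1.
- Power from the noncentral t: 91.0%. At 22 per arm it is 89.7%, so 23 per arm (46 in total) is confirmed.

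**3. Evaluable range.** Enrollment is 65 to 100 with nearly 30% dropout. 46/(1 − 0.29) = 64.8, so 65 enrolled gives about 23 per arm. 100 × 0.70 = 70, so 100 enrolled gives about 35 per arm.

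**4. Illustrate dilution.** The documents give no rate of non-study use, so a share c of placebo patients is assumed, each getting a fraction e of the 2-day effect. Use in the active arm is assumed to change nothing. The expected difference is 2(1 − ce), with SDs held at 1.3 and 2.5.

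| Per arm | Effect in users | c = 0 | c = 10% | c = 20% |
|---|---|---|---|---|
| 23 | full (e = 1) | 91.0% | 84.5% | 75.3% |
| 23 | half (e = 0.5) | 91.0% | 88.1% | 84.5% |
| 35 | full (e = 1) | 98.5% | 96.0% | 90.9% |

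The expected differences are 1.8 and 1.6 days at full effect, and 1.9 and 1.8 days at half effect.

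**5. Check the SD assumption.** If the placebo SD follows the mixture, √[(1 − c)2.5² + c·1.3² + c(1 − c)2²], it is 2.48 at c = 10% and 2.44 at c = 20%. Power at 23 per arm with full effect is then 84.9% and 76.8%, which gives the ranges 84.5–84.9% and 75.3–76.8%.

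**The case against.** **The rule exists; only the form lacks it.** Exclusion 6 is in force in section 4.2. Charts are screened for eligibility (4.3), section 6.2 requires eligibility to be confirmed, and the enrollment form asks about supplements. A patient who passes the checklist is therefore not necessarily enrolled. This stands, and it limits the point to a mismatch between form and protocol. It does not remove it: a chart may not show a product bought over the counter, and the supplement list neither names elderberry nor feeds the eligibility tick.

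**Follow-up is partly covered.** A reader might infer that the plan lets placebo patients take elderberry freely after entry and that no follow-up rule mentions it. The documents do not support that. Elderberry syrup taken for influenza can reasonably be read as a cold or flu preparation, which section 5.6 discourages, and the daily form captures herbal products and supplements. The absence of elderberry by name from the follow-up rules is verified only for the protocol body and forms 14.1 and 14.2. The handout (14.3) and take-home checklist (14.4) were not available.

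**Sections 4.2 and 6.2 do not conflict on later use.** Exclusion 6 is an entry criterion, and keeping patients who take other products later fits an intent-to-treat plan. This stands. What needs reconciling is the treatment of use before entry.

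**The power loss may be small.** The larger losses combine an assumed rate, the full effect in every user and the smallest evaluable size. This also stands, and the table shows how far the loss shrinks when the second or third is relaxed. A larger sample restores power but not the diluted estimate.

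**Conclusion.** The mismatch is a fact of the text: form 14.1 omits exclusion 6, and a correctly completed form can pass a patient whom section 4.2 excludes. It should be corrected. The follow-up wording is a matter of clarification.

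The consequence is conditional. It requires that current users are enrolled, that some are assigned to placebo and continue, and that elderberry works. On those assumptions, 10% to 20% use in the placebo arm costs about 6 to 16 percentage points of power at 23 per arm with full effect, about 3 to 6.5 points with half the effect, and about 2.5 to 7.5 points at 35 per arm with full effect. Nothing in the documents shows that such use will occur or how often, so the figures should not be read as a forecast that the trial is underpowered.

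**What to change.** - **Form 14.1:** add exclusion 6 as an eighth line above the confirmation box, worded as in section 4.2.
- **Section 6.2:** reconcile its statement of what disqualifies a patient before the start with exclusion 6.
- **Section 5.6:** state whether non-study elderberry products fall under the preparations that patients are discouraged from taking, and check that attachments 14.3 and 14.4 agree.
- **Section 7.2:** add a sentence that elderberry use reported on the daily form will be summarised by arm, with those patients kept in the intent-to-treat analysis.

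The cost is one line on a form and a few phrases in the protocol. Some patients may be screened out who would otherwise have passed the form, but they are already ineligible under section 4.2. The target of 46 evaluable patients is unchanged.
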